6.4 Unscheduled Visits

• Record reason on the Unscheduled Visit CRF

6.5 Subject Withdrawal

As this is a real-world pragmatic study, patients should be encouraged to continue in the study regardless of their response or adherence to phototherapy. Participants may withdraw from the study at any time without impact to their care. They may also be discontinued from the study at the discretion of the site investigator for lack of adherence to study procedures, or visit schedules, or for safety or administrative concerns. Reasons for withdrawing a subject from the study will be documented by the investigator. Patients withdrawn after randomization will not be eligible for rescreening. Patients withdrawn prior to randomization may be rescreened with the approval of the PI ([name]). Subjects withdrawn for loss to follow up should have been called by phone at least 3 times and have a certified letter sent to the subject requesting information necessary to complete the withdrawal process. If the subject does not contact the site within 30 days of sending of the certified letter, they will be defined as lost to follow up.

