3.2 Study Endpoints

3.2.1 Primary Study Endpoints

The first primary effectiveness outcome is treatment response, a dichotomous indicator of whether a patient has achieved clear/almost clear skin (score of 0 or 1), based on the Physician's Global Assessment (PGA) at the earlier of week 12 or discontinuation of phototherapy. See Appendix B for PGA tool.

The second co-primary outcome is the patient-reported Dermatology Life Quality Index (DLQI) at week 12. We will dichotomize DLQI at a score of 0-5 (corresponding to no to small impact on quality of life) versus a score $\ge 6^{44}$.

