5.7 Subject Compliance Monitoring

Compliance will be measured by evaluating the number of study treatments received. Patients receiving home phototherapy will have this recorded by the home phototherapy device. Home phototherapy treatments will be verified via software obtained from the device upon their return to Daavlin. The data obtained from the devices will be considered the primary data for analysis. Patients randomized to office based phototherapy will have their treatments entered by the site staff. It is expected that patients will receive up to 36 treatments. Patients who receive at least 29 treatments will be viewed as compliant for the purposes of sensitivity analyses.

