6.2 Study Intervention Phase Weeks 1-12

6.2.1 Week 1

- Administer NB-UVB phototherapy three times per week
- Patient reported DLQI (complete prior to first phototherapy treatment)
- Patient reported target lesion image taken prior to first treatment
- Patient reported psoriasis topical treatment
- Patient reported response to phototherapy prior to treatments. For those on office treatment, data is entered by the sites. For those on home treatment, data is recorded on the home device.
- Phototherapy session number and dose. For those on office treatment, data is entered by the sites. For those on home treatment, data is recorded on the home device

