7.6 Safety Evaluations

Safety will be monitored by the local clinicians.

Patients will be queried about the reaction to phototherapy (i.e., burns) immediately prior to each phototherapy treatment as is standard practice. Patients will contact the study clinicians for any significant reaction to phototherapy (a burn which requires medical attention such as one associated with significant pain that interrupts usual activities or skin blistering). Patients will be queried about SAE's at visit 2. Patients can spontaneously report SAEs at any point during the study.

8 Statistical Plan

8.1 **Primary Endpoint**

Primary analyses will be based on the intent to treat (ITT) population defined as all patients meeting eligibility requirements who are randomized to one of the two study arms. In the ITT population, we will compare the two treatment arms with respect to two primary effectiveness outcomes. The first primary effectiveness outcome is treatment response, a dichotomous indicator of whether a patient has achieved clear/almost clear skin (score of 0 or 1), based on the Physician's Global Assessment (PGA) at the earlier of week 12 (visit 2), defined as the twelfth week after the start of treatment, or the time of discontinuation of phototherapy. In our primary analyses, patients who drop out of the study prior to achieving clear/almost clear skin or week 12, whichever comes first, will be classified as treatment failures (i.e., failure to achieve clear/almost clear skin). The second primary outcome is the patient-reported Dermatology Life Quality Index (DLQI) assessed at week 12. We will dichotomize DLQI at a score of 0-5 (corresponding to no to small impact on quality of life) versus a score >5. Patients failing to complete the week 12 DLQI assessment will be assumed to have DLQI >5 and therefore classified as a non-responder on this measure.

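### Section 6.5 both protects and allows removal of poorly adherent patients; removal nearly always scores as a co-primary failure, so removals that differ by arm would bias the non-inferiority comparison

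*Combined protocol and SAP*

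**What the plan says.** Section 6.5 (Subject Withdrawal) opens with a pragmatic principle: "patients should be encouraged to continue in the study regardless of their response or adherence to phototherapy". It then allows a participant to end up "discontinued from the study at the discretion of the site investigator for lack of adherence to study procedures, or visit schedules". Concerns about safety or administration are further grounds. The section gives no threshold for non-adherence and no definition that works the same way in both arms. Section 6.2, under the heading Study Procedures, lists "Administer NB-UVB phototherapy three times per week" for the treatment weeks.

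Section 8.1 sets the consequence. For PGA, those that "drop out of the study prior to achieving clear/almost clear skin or week 12, whichever comes first, will be classified as treatment failures". For DLQI, "Patients failing to complete the week 12 DLQI assessment will be assumed to have DLQI >5". Section 3.2.1 times the first co-primary outcome as the "Physician's Global Assessment (PGA) at the earlier of week 12 or discontinuation of phototherapy". Section 8.5 keeps all randomized subjects in the primary analysis. Section 6.5.1 covers only participants who withdraw consent, and asks them only for the reason.

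On recording of sessions, section 5.7 has site staff enter office treatments, whereas "Home phototherapy treatments will be verified via software obtained from the device upon their return to Daavlin".

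**The concern.** The trial asks how two treatment settings perform under ordinary adherence, so partial adherence is part of what is being compared. If a site can take a patient out of the study for poor adherence, and removal is scored as failure, the site's decision can replace the patient's outcome. The decision is made with the arm known, because the site prescribes the home unit (section 5.6) or schedules and enters the office sessions.

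Scoring removed patients as failures is not automatically conservative in a non-inferiority comparison. Failures that fall more heavily on the office arm lower the reference rate and make non-inferiority of home easier to show. Failures that fall more heavily on home do the opposite. Both distort the estimate, and a false conclusion of non-inferiority is the more serious error.

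**Working it through.** **1. Does a removed patient become a failure?**
- Denominator: the patient remains in it (sections 8.1 and 8.5).
- DLQI: the endpoint is fixed at week 12. If that score is missing, the patient is a non-responder.
- PGA: the patient fails unless clear or almost clear skin was recorded at an assessment made when phototherapy stopped (sections 3.2.1 and 6.2.5). Such a patient can be a PGA responder and still fail DLQI.
- Recovery of data: no section provides for outcome collection after site-initiated removal.

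**2. Do the planned analyses catch it?** Section 8.4.5 states that the two primary outcomes will have no missing data, then plans a tipping-point analysis for missing measures. It is unclear whether that analysis reaches patients already scored as failures. The as-treated analysis (sections 8.4.4 and 8.5) keeps completers with at least 80% of treatments, so it cannot recover them.

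**3. Reproduce the plan's own figures (section 8.3).** Inputs: 50% response in both arms, margin 15 points, one-sided alpha 2.5%, power 80%.

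n per arm = (1.960 + 0.842)² × (0.5×0.5 + 0.5×0.5) / 0.15² = 7.85 × 0.5 / 0.0225 ≈ 174.4, rounded up to 175. This matches. The same formula gives 80.1% power at 175 per arm. Section 3.1 anticipates 350 + 350 + about 80 = about 780 patients, or 390 per arm, with power 98.7%. The target of 1050 gives 525 per arm, with power 99.8%. Both agree with the stated 99%.

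**4. Size of the shift.** Let r be the excess share of office patients removed. Let q be the share of them who would otherwise have supplied an outcome and counted as responders. The documents give neither; the ranges below are assumptions.

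Shift toward home = r × q. Smallest: 0.02 × 0.20 = 0.4 points. Largest: 0.10 × 0.50 = 5.0 points. Against the margin: 0.4/15 = 3% and 5.0/15 = 33%.

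**5. Chance of a false non-inferiority conclusion.** Take home truly 15 points worse (office 50%, home 35%), where the nominal error is 2.5%. With p_o = 0.50 − r×q, p_h = 0.35 and SE = √{[p_o(1−p_o) + p_h(1−p_h)]/n}, the chance is Φ{[0.15 − (p_o − p_h)]/SE − 1.96}. This is an unadjusted normal approximation.

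Example at 390 per arm, r = 5%, q = 0.35: p_o = 0.4825, SE = 0.0350, and Φ(0.0175/0.0350 − 1.96) = Φ(−1.46) = 7.2%.

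Results at 390 per arm (shift in points; error):

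| r | q = 0.20 | q = 0.35 | q = 0.50 |
|---|---|---|---|
| 2% | 0.4; 3.3% | 0.7; 3.9% | 1.0; 4.7% |
| 5% | 1.0; 4.7% | 1.75; 7.2% | 2.5; 10.7% |
| 10% | 2.0; 8.3% | 3.5; 16.9% | 5.0; 29.9% |

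At 175 per arm (one skin-type stratum) the same grid runs from 3.0% to 15.9%.

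**6. Direction.** With q = 0.35 and 390 per arm:
- 5% removed in each arm: error stays at 2.5%.
- 10% office, 5% home: 7.3%.
- 5% office, 10% home: 0.7%.

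**The case against.** The strongest reply is that section 6.5 can be read without contradiction. The protective sentence concerns adherence to phototherapy; the removal clause concerns procedures and visit schedules. Section 13.3 counts only two study visits, plus app questionnaires every four weeks, and these are the same in both arms. On that reading missed phototherapy is not a ground for removal and exposure to the rule is equal. The reading is possible, but section 6 puts the sessions under study procedures, so a site could reasonably read the clause the other way. The ambiguity itself needs resolving.

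A reader might go further and infer that missed sessions are visible as they happen only in the office arm, so that the rule favours home. The documents do not support this as fact. They do point that way: office patients are questioned by staff and home patients by the machine (section 3.2.3), and the device goes back after treatment (section 5.7.1). But nothing says that sites cannot see home sessions earlier, and sections 9 and 9.2 have site personnel reviewing patients' response to treatment without separating the arms.

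Two further points stand. Many patients removed for missing visits would have supplied no outcome and been scored as failures anyway, and poor adherers probably respond less often; both push q down, and 50% equals the planning rate for all patients. Also, section 6.5 requires withdrawal reasons to be documented, so removals can be tabulated by arm.

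**Conclusion.** The point holds as a conditional risk of bias, not as an error of arithmetic. The plan's sample size and power reproduce and are unaffected. What the documents establish is the conflict within section 6.5, the near-automatic scoring of removed patients as failures, and the absence of any provision for collecting their outcomes. What they do not establish is the rate of removal, its imbalance or its direction. A stronger claim, that the rule will bias the trial toward home by a known amount, would rest wholly on assumed inputs. Within the ranges shown, the effect runs from negligible to a third of the margin; it vanishes if removals and counterfactual response are equal in the two arms, and reverses if home patients are removed more often. Because the decision is discretionary and made with the arm known, and the remedy is cheap, the text should be changed.

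**What to change.** - **Section 6.5:** reconcile the two sentences so that non-adherence to phototherapy or to visits is not a ground for site-initiated discontinuation from the study. Leave withdrawal of consent, and safety and administrative grounds, as they are. The change concerns follow-up status only, not whether phototherapy continues. Because section 5.6 ties withdrawal from the study to return of the home device, check the two sections for consistency.
- **Section 6.5.1:** state that Visit 2 PGA and week 12 DLQI are sought for every randomized patient who has not withdrawn consent, whatever their adherence.
- **Section 8.4.5:** report site-initiated removals by arm and reason, and add a sensitivity analysis that does not impute failure for them. Extending the planned tipping-point analysis explicitly to these patients would serve.

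Cost: a short amendment, with no new visits and no change in sample size. Sites would have to follow up some poorly adherent patients for one visit and the app questionnaires.

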6.5.1 Data Collection and Follow-up for Withdrawn or Early Termination Participants

Participants who withdraw consent to participate in the study will be asked to report the reason for withdrawal.

7 Study Evaluations and Measurements

The data collected in this study are all considered relevant for routine clinical care. In routine clinical care, there is some variation in which assessments are conducted and thus we will standardize assessments for the purpose of the study.

Investigator reported measures:

1. Physicians Global assessment (PGA): This is a three item measure that asks the physician or his or her designee to assess the thickness, redness, and scale of psoriasis plaques.

2. Body Surface Area (BSA): This is a measure that asks the physician or his or her designee to assess the body surface area affected by psoriasis using the handprint method in which the palm of the entire hand approximates 1% of the body surface area. To do this, the patient's handprint, including the entire area of the palm and all 5 digits with the fingers close together but not overlapping, is used as a guide to estimate 1% of the BSA

3. Number of phototherapy treatments and dose received: This data is routinely collected in clinical practice. It will be reported by the sites for patients receiving office treatment and will be obtained from the machines for those receiving home based treatment

- 4. Copay for office-based phototherapy
- 5. Concomitant treatment

Patient reported measures:

1. Dermatology Life Quality Index: (DLQI): DLQI is a 10 item survey that asks patients questions about their health related quality of life on a 0-3 scale. DLQI is routinely used in clinical trials of psoriasis treatments and can also be used routinely in clinical practice.

2. Patient reported response to phototherapy: This is a standard question asked to the patient to document the degree and duration of erythema induced by the prior phototherapy treatment session. It is standard of care.

- 3. Patient reported time spent on travel, cost of travel, and time spent on phototherapy
- 4. Patient reported concomitant psoriasis topical treatment

5. Photograph of target psoriasis lesion (at a subset of study sites)

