10.1 Confidentiality

Information about study subjects will be kept confidential and managed according to the requirements of the Health Insurance Portability and Accountability Act of 1996 (HIPAA). Those regulations require a signed subject authorization informing the subject of the following:

- What protected health information (PHI) will be collected from subjects in this study
- Who will have access to that information and why

- Who will use or disclose that information
- The rights of a research subject to revoke their authorization for use of their PHI.

In the event that a subject revokes authorization to collect or use PHI, the investigator, by regulation, retains the ability to use all information collected prior to the revocation of subject authorization. For subjects that have revoked authorization to collect or use PHI, attempts should be made to obtain permission to collect at least vital status (i.e. that the subject is alive) at the end of their scheduled study period.

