10.2 Data Collection and Management

Patients will complete an electronic consent and HIPAA form and data will be collected via an app developed using Medable software. The app will reside on a tablet device at each site (for site entered data) and on the patient's smart phone (a smart phone will be provided for the purposes of the study to patients who do not have one). Data will be encrypted and housed on a cloud-based server operated by Google Cloud Platform and is compliant with 21 CFR Part 11, HIPAA and international privacy regulations and laws. Personally identifiable information (PII) and protected health information (PHI) will be housed in the app's account record which is separate from the study database (task and step responses from electronic case report forms (eCRFs)). Access to data collected via the app is only granted to the researchers who create the App and if other researchers would like to access the data, only the aforementioned App creators may grant this through user authentication. Authentication is available through session-based, signature-based, and single-factor authentication. Access to data, once authenticated, is managed via fine-grained access control lists. The research team may securely download and transfer data from Medable. PII and PHI will not be available to access with standard tools of data exports. PII and PHI will only be accessible to research team members with administrator roles and assignments of scripts to pull the select PII and/or PHI as needed.

All participants will receive a random identification number that will be used to identify participants' data. No direct identifiers will be used.

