13.3 Subject Stipends or Payments

Subjects will be asked to complete two study visits, Baseline and End of Intervention. These study visits will occur in conjunction with standard of care clinical visits that subjects would already attend. Subjects will not be reimbursed for time, travel, parking, copays, deductibles, or any other costs associated with study participation.

Subjects will be asked to complete questionnaires via a mobile app every four weeks starting from randomization and ending at the End of Observation Period for a total of eight times. For each questionnaire, subjects will be reimbursed \$20 after questionnaire completion. Subjects who do not have access to a smart phone will be provided one throughout study duration at no cost.

If the subject does not complete all questionnaires, the amount received will be pro-rated to reflect the number questionnaires completed. In addition, subjects may need to complete a W-9 form which is required by the IRS when study participation will result in a subject receiving more than \$600 in a calendar year. This form will be provided for subjects.

14 Publication Plan

The study PI, [name], holds the primary responsibility for publication of the results of the study. Permission must be obtained from [name] before any study related information can be used or passed on to a third party.

15 References

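### No visible section asks for the week 12 DLQI from participants who leave the study, including those the site discontinues, and each one is then scored as a non-responder

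*Combined protocol and SAP*

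**What the plan says.** **Leaving the study.** Section 6.5.1, whose title covers both withdrawn and early-terminated participants, contains one instruction: "Participants who withdraw consent to participate in the study will be asked to report the reason for withdrawal". Section 6.5 opens by saying that "patients should be encouraged to continue in the study regardless of their response or adherence to phototherapy", then adds: "They may also be discontinued from the study at the discretion of the site investigator for lack of adherence to study procedures". It also allows discontinuation for visit-schedule, safety or administrative reasons. For people who revoke authorization, 10.1 keeps the data already collected and says that "attempts should be made to obtain permission to collect at least vital status".

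**Stopping treatment.** This is handled separately. Section 6.2.5 holds Visit 2, with PGA and DLQI, at discontinuation of phototherapy if that precedes week 12. Section 3.1.2 assigns a start date to patients who have not begun by day 14, and 8.5 analyses everyone randomized.

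**How the DLQI is collected.** Section 13.3: "Subjects will be asked to complete questionnaires via a mobile app every four weeks", up to the end of the observation period, at $20 each. Section 10.2 adds that "a smart phone will be provided for the purposes of the study to patients who do not have one".

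**How missing outcomes are scored.** Section 8.1: "Patients failing to complete the week 12 DLQI assessment will be assumed to have DLQI >5". Dropout before response or week 12 is a PGA failure. Section 8.4.5 concludes that the co-primary outcomes have no missing data, and plans a tipping-point analysis without naming the outcomes it covers.

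**The concern.** The DLQI is a ten-item patient survey that needs neither a clinician nor treatment. A participant taken off study by the site for poor adherence or missed visits may not have withdrawn consent and may be willing to answer it, as may some of those who withdraw. The plan does not ask either group, and 8.1 converts the gap into a failure.

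In a superiority trial that scoring is often defended as conservative. Here it is not reliably so. Equal withdrawal multiplies both response rates by the same factor and pulls the arms together, which favours a non-inferiority conclusion. Unequal withdrawal creates or hides a difference unrelated to the effect of treatment. Some imbalance is plausible: home treatment is free (12.2), while office patients are not reimbursed for travel or co-pays (13.3).

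**Working it through.** **Inputs from Section 8.3:** response 50% in both arms, margin 15 points, one-sided 2.5%, 175 per arm per skin type, 80% power. Pooled size per arm is 1050/2 = 525 at the full target. With the roughly 80 type V/VI patients anticipated in 3.1 it is (350 + 350 + 80)/2 = 390.

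**The plan's own figure.** n = 2(0.5)(0.5)(1.96 + 0.8416)²/0.15² = 174.4, so 175 per arm with power 80.1%. This reproduces. The same formula gives pooled power of 98.7% at 390 and 99.8% at 525, in line with the stated 99%.

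**Assumptions not in the documents:** a withdrawal fraction d of 5 to 20%, and leavers who would have responded like everyone else. If every leaver is scored a failure, the observed rate is p(1 − d). With

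SE = √{[p_o(1 − p_o) + p_h(1 − p_h)]/n},

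the probability of declaring non-inferiority is Φ([0.15 − (p_o − p_h)]/SE − 1.96).

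**Equal withdrawal, true rates 50% office and 35% home (exactly at the margin):**

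| d | Observed office / home | Observed deficit (points) | Error, 175 per arm | 390 | 525 |
|---|---|---|---|---|---|
| 0 | 50.0 / 35.0% | 15.0 | 2.5% | 2.5% | 2.5% |
| 5% | 47.5 / 33.25% | 14.25 | 3.5% | 4.1% | 4.4% |
| 10% | 45.0 / 31.5% | 13.5 | 4.8% | 6.4% | 7.3% |
| 15% | 42.5 / 29.75% | 12.75 | 6.5% | 9.7% | 11.6% |
| 20% | 40.0 / 28.0% | 12.0 | 8.7% | 14.3% | 17.7% |

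Example at 15% and 175 per arm: SE = √[(0.425 × 0.575 + 0.2975 × 0.7025)/175] = 0.0509, and Φ(0.0225/0.0509 − 1.96) = Φ(−1.518) = 6.5%.

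Power under true equality is not harmed when withdrawal is equal: 80.1% at d = 0 and 81.7% at d = 20%.

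**Unequal withdrawal, 175 per arm:**
- Office 15%, home 5%, no true difference: 0.5 × 0.95 − 0.5 × 0.85 = +5.0 points for home, a third of the margin. With a true 15-point deficit, error is 19.9%.
- Office 5%, home 15%, no true difference: −5.0 points, and power falls from 80% to 47%.

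**Partial recovery.** If 15% leave in each arm but half of them answer the week 12 DLQI, 7.5% remain missing. The deficit is 15 × 0.925 = 13.9 points, and error is 4.1% at 175 and 5.1% at 390 per arm.

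**Leavers who respond less often.** Suppose leavers respond at half the stayers' rate, with overall true rates held at 50% and 35%. Stayers then respond at p/(1 − d/2), and the observed rate is p(1 − d)/(1 − d/2). At d = 5% this is 48.7% versus 34.1%, and error at 175 per arm is 3.0%. At d = 20% it is 44.4% versus 31.1%, and error is 5.1%. The direction is unchanged and the size is smaller.

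**The case against.** A reader might infer that the plan gives a patient who stops treatment no option short of leaving the study. The documents do not support that. Stopping phototherapy is not withdrawal: such patients are encouraged to stay, have Visit 2, and keep the app questionnaires to the end of observation. The gap concerns study withdrawal and site discontinuation only.

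Other points on that side, and what stands:

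- **The 6.5.1 sentence concerns withdrawn consent.** Those people cannot be followed without permission, and asking only for a reason respects that. This stands, and it is why anything added must be voluntary. It does not cover site-discontinued participants, whom 6.5.1 omits despite its title.
- **Vital status is a minimum in 10.1, not a cap.** Correct, but nothing beyond it is planned. The calls and certified letter in 6.5 seek what is needed to complete the withdrawal process, not outcomes.
- **The appendices were not available.** The consent and assent forms, schedule and monitoring plan are listed in Section 16, but their content is not in the text reviewed. Levels of withdrawal may be set out there, so the claim is limited to the visible sections.
- **Phone completion of the Visit 2 DLQI is not stated.** Section 6.2.5 gives no mode for it, while marking the travel and time items as site-administered. With 10.2 and 13.3, the app is a strong inference but still an inference. It does not extend to the PGA, which needs a clinician.
- **Differential withdrawal is partly guarded against.** Section 3.1.1 confirms willingness after co-pays are known and before randomization, and 4.2 excludes patients who could not comply with either arm. This lowers the likelihood of imbalance without removing it.
- **The harm comes from the scoring rule, and a tipping-point analysis is planned.** True, but that analysis does not replace data that could have been collected, and 8.4.5 does not say that it covers the co-primaries.
- **Silent non-completers and those lost to follow-up would not be recovered.** This stands.

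**Conclusion.** The concern holds in a limited form. The visible plan has no step to obtain the week 12 DLQI from participants who leave the study. The clearest omission is people the site discontinues who have not withdrawn consent. Section 8.1 then scores them as non-responders, which in a non-inferiority comparison can favour home treatment when withdrawal is equal and can push either way when it is not.

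The size is unknown, because no withdrawal rate is stated. The figures of 3.5 to 8.7% error at 175 per arm, and about 5 points for a 10-point imbalance, are upper illustrations. They assume that leavers would respond like stayers. They also compare scoring every leaver as a failure with recovering every outcome. The sample size of 175 per arm is not in question and does not change. The amendment is worth making because these data can be obtained only while participants are still reachable.

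**What to change.** In Section 6.5.1:

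1. For participants discontinued by the site who have not withdrawn consent, continue the app questionnaires, at minimum the week 12 DLQI.
2. Before recording full withdrawal, offer the option of leaving visits while keeping the week 12 DLQI, and request a PGA if the participant agrees.
3. Record the level of withdrawal on the CRF.

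In Section 10.1, ask permission for the week 12 DLQI alongside vital status. In 8.4.5, state that the tipping-point analysis covers both co-primary outcomes.

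All of this is voluntary for the participant. The cost is a protocol amendment with IRB review, possible consent wording across 20 to 40 sites, one CRF field, any app change needed to keep the questionnaire open, and some extra $20 payments. The app, phone provision and payment scheme already exist.
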